### 9.3 SAFETY

**Table 9.15 Physical examination. Safety population. N = xx**

Category	Levopront® (T) n (%) N = XX	Libexin® (C) n (%) N = XX	p-value
Screening (baseline). Day 1			0.xxx
General appearance			
Normal	xx (xx.x%)	xx (xx.x%)	
Abnormal	xx (xx.x%)	xx (xx.x%)	
Not done	xx (xx.x%)	xx (xx.x%)	
Eyes, ears, nose, throat			
Normal	xx (xx.x%)	xx (xx.x%)	
Abnormal	xx (xx.x%)	xx (xx.x%)	
Not done	xx (xx.x%)	xx (xx.x%)	
Neck (including thyroid)			
Normal	xx (xx.x%)	xx (xx.x%)	
Abnormal	xx (xx.x%)	xx (xx.x%)	
Not done	xx (xx.x%)	xx (xx.x%)	

Category	Levopront® (T) n (%) N = XX	Libexin® (C) n (%) N = XX	p-value
.. Day 4			0.xxx
... Day 8/ET or ED			0.xxx
...			

Table 9.16 Vital signs. Safety population. N = xx

	Levopront® (T) N = XX	Libexin® (C) N = XX
Day 1 (baseline)		
Body temperature (°C)		
N	xx	xx
Mean (SD)	xx.x (xx.x)	xx.x (xx.x)
Median	xx.x	xx.x
Min - Max	xx.x - xx.x	xx.x - xx.x
Heart rate (beats/min)		
N	xx	xx
Mean (SD)	xx.x (xx.x)	xx.x (xx.x)
Median	xx.x	xx.x
Min - Max	xx.x - xx.x	xx.x - xx.x
Respiratory rate (/min)		
N	xx	xx
Mean (SD)	xx.x (xx.x)	xx.x (xx.x)
Median	xx.x	xx.x
Min - Max	xx.x - xx.x	xx.x - xx.x
Systolic blood pressure (Hg mm)		
N	xx	xx
Mean (SD)	xx.x (xx.x)	xx.x (xx.x)
Median	xx.x	xx.x
Min - Max	xx.x - xx.x	xx.x - xx.x
Diastolic blood pressure (Hg mm)		
N	xx	xx
Mean (SD)	xx.x (xx.x)	xx.x (xx.x)
Median	xx.x	xx.x
Min - Max	xx.x - xx.x	xx.x - xx.x
Day 4		
...		
Day 4. Change from baseline		
N	xx	xx
Mean (SD)	xx.x (xx.x)	xx.x (xx.x)
Median	xx.x	xx.x
Min - Max	xx.x - xx.x	xx.x - xx.x
p-change	0.xxx	0.xxx
Day 8/ET or ED		
...		
Day 8/ET or ED. Change from baseline		
...		

**Table 9.17 Urine pregnancy test (females only). Safety population. N = xx**

	Levopront® (T) n (%) N = XX	Libexin® (C) n (%) N = XX
Screening (Day 1)		
Positive	xx (xx.x%)	xx (xx.x%)
Negative	xx (xx.x%)	xx (xx.x%)
No data	xx (xx.x%)	xx (xx.x%)
Day 8/ED		
Positive	xx (xx.x%)	xx (xx.x%)
Negative	xx (xx.x%)	xx (xx.x%)
No data	xx (xx.x%)	xx (xx.x%)

**Table 9.18 Concomitant medication. Safety population.  
During the study. N = xx**

ATC code Drug	Levopront® (T) n (%) N = XX	Libexin® (C) n (%) N = XX
Group		
Total	xx (xx.x%)	xx (xx.x%)
DRUG (ATC)	xx (xx.x%)	xx (xx.x%)
...		

**Table 9.19 Laboratory parameters. Hematology. Deviation from normal values.  
Safety population. N = xx**

Parameter	Day 1		Day 8/ET	
	Levopront®	Libexin®	Levopront®	Libexin®
Hemoglobin				
No data	xx (xx.x%)	xx (xx.x%)	xx (xx.x%)	xx (xx.x%)
CNS deviation	xx (xx.x%)	xx (xx.x%)	xx (xx.x%)	xx (xx.x%)
CS deviation	xx (xx.x%)	xx (xx.x%)	xx (xx.x%)	xx (xx.x%)
Normal	xx (xx.x%)	xx (xx.x%)	xx (xx.x%)	xx (xx.x%)
Hematocrit				
No data	xx (xx.x%)	xx (xx.x%)	xx (xx.x%)	xx (xx.x%)
CNS deviation	xx (xx.x%)	xx (xx.x%)	xx (xx.x%)	xx (xx.x%)
CS deviation	xx (xx.x%)	xx (xx.x%)	xx (xx.x%)	xx (xx.x%)
Normal	xx (xx.x%)	xx (xx.x%)	xx (xx.x%)	xx (xx.x%)
...				

**Parameters to be presented:** Hemoglobin, Hematocrit, RBC, WBC, Neutrophils (abs), Lymphocytes (abs), Monocytes (abs), Eosinophils (abs), Basophils (abs), Platelets, ESR, Neutrophils (%), Lymphocytes (%), Monocytes (%), Eosinophils (%), Basophils (%).

**Table 9.20 Laboratory parameters. Hematology. CS deviations only. Safety  
population. N = xx**

Parameter	Day 1		Day 8/ET	
	Levopront®	Libexin®	Levopront®	Libexin®
Hemoglobin				
CS deviation	xx (xx.x%)	xx (xx.x%)	xx (xx.x%)	xx (xx.x%)
Hematocrit				
CS deviation	xx (xx.x%)	xx (xx.x%)	xx (xx.x%)	xx (xx.x%)
...				
p-value 		0.xxx		0.xxx

**Table 9.21 Laboratory parameters. Biochemistry. Deviation from normal  
values. Safety population. N = xx**

Parameter	Day 1		Day 8/ET	
	Levopront®	Libexin®	Levopront®	Libexin®
Total protein				
No data	xx (xx.x%)	xx (xx.x%)	xx (xx.x%)	xx (xx.x%)

 For the set of parameters at visit

Parameter	Day 1		Day 8\ET	
	Levopront®	Libexin®	Levopront®	Libexin®
CNS deviation	xx (xx.x%)	xx (xx.x%)	xx (xx.x%)	xx (xx.x%)
CS deviation	xx (xx.x%)	xx (xx.x%)	xx (xx.x%)	xx (xx.x%)
Normal	xx (xx.x%)	xx (xx.x%)	xx (xx.x%)	xx (xx.x%)
Albumin				
No data	xx (xx.x%)	xx (xx.x%)	xx (xx.x%)	xx (xx.x%)
CNS deviation	xx (xx.x%)	xx (xx.x%)	xx (xx.x%)	xx (xx.x%)
CS deviation	xx (xx.x%)	xx (xx.x%)	xx (xx.x%)	xx (xx.x%)
Normal	xx (xx.x%)	xx (xx.x%)	xx (xx.x%)	xx (xx.x%)
...				

**Parameters to be presented:** Total protein, Albumin, Total cholesterol, Total bilirubin, Conjugated bilirubin, ALT, AST, Serum creatinine, Glomerular filtration rate.

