3.2 Justification of Study Design

This is an open-label randomized comparative clinical trial of the efficacy and safety of Levopront®, syrup 30 mg/5 mL and Libexin®, tablets 100 mg in patients with dry non-productive cough associated with acute respiratory infection of upper airways.

Patients from reference group will receive Libexin®. The choice of Libexin® is based on the similarity of its mechanism of action (it is a peripheral antitussive drug) and on the fact that it belongs to the same group in the International anatomical therapeutic chemical classification. Open design was chosen because of differences in the pharmaceutical forms of the investigational drugs and technical problems with blinding process of investigational products.

Study population includes patients with dry non-productive cough associated with non-complicated acute respiratory infection of upper airways. At Visit 1, Day 1 patients meeting inclusion/exclusion criteria will be enrolled into the study. During that period patients will receive either Levopront®, syrup 30 mg/5 mL or Libexin®, 100 mg tablets along with standardized concomitant treatment allowed by this protocol for 7 days, if necessary. Patients will keep a diary where they will record their condition using a "Six-point daytime and nighttime cough assessment scale". Assessment of the cough intensity with the visual-analogue scale will be done on each visit of the patients at the clinical site.

Patients with severe and chronic diseases of the respiratory system, burdened with smoking anamnesis, as well as patients who have indicated administration of the antibacterial therapy will not be included in the study.

Study drug dosing regimen and treatment duration of 7 days were chosen according to the European label. The treatment duration is necessary and sufficient to establish control over efficacy of antitussive therapy (frequency of resolution of cough symptoms) in acute respiratory infections of the upper respiratory tract. The intermediate evaluation of the efficacy will be held on Day 4.

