6.11 Tests Performed at Local Laboratory

Local laboratory will be used for laboratory tests. Collection, preparation and storage of biological samples will meet requirements of the study site local laboratory.

At baseline, all local laboratories will provide the required certificates and laboratory reference values. Local laboratory is responsible for sending laboratory reports to the Investigator, and for reporting abnormal laboratory values to the Investigator. Investigator should review the laboratory report, all abnormal values should be assessed, signed and dated. Deviations of laboratory values from baseline, reported as AEs should be appropriately reported in the source documentation and in CRF.

Patient randomization is performed before laboratory test results are available. In case of significant abnormality which, at the Investigator's opinion, could interfere with patient's participation in the study or impact interpretation of efficacy or safety parameters, the patient should be withdrawn from the study.

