6.12.11 Clinically Significant Laboratory Abnormalities

Any clinically significant abnormalities of laboratory parameters or results of the instrumental methods of examination noted at screening shall be registered in the patient's medical history. After screening, new or worsened clinically significant abnormalities shall be reported as adverse events in source documents and CRF.

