#### **7.3.2 Laboratory Data**

Laboratory data will be summarized by treatment group as clinical relevance (normal/abnormal, without clinical relevance/ abnormal, with clinical relevance) and as continuous data (absolute values).

All laboratory data and changes from baseline will be described as continuous variables at each visit.

Treatment groups will be compared for the set of parameters (hematology set, biochemistry set, urinalysis set and microscopic urine examination set). Only clinically significant deviations (CS) will be taken into account. Permutation test will be used see 8 [2].

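### The only between-arm laboratory p-values rest on clinical-significance labels set, without stated criteria, by an investigator who knows the arm, and the shells do not separate high from low

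*SAP*

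**What the plan says.** SAP 7.3.2 sets the unit of comparison: "Treatment groups will be compared for the set of parameters (hematology set, biochemistry set, urinalysis set and microscopic urine examination set"). It then restricts what counts: "Only clinically significant deviations (CS) will be taken into account". The method is a permutation test.

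The shells match. The p-value row in "Table 9.20 Laboratory parameters. Hematology. CS deviations only" carries the footnote "For the set of parameters at visit", so there is one p-value per panel at Day 1 and one at Day 8. Tables 9.22, 9.24 and 9.26 have the same layout. Each has a single CS row per parameter, with no split by direction.

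The CS label comes from the investigator. Protocol 6.11 says: "Investigator should review the laboratory report, all abnormal values should be assessed, signed and dated". The SAP abbreviation list expands CS, and Protocol 6.12.11 uses the term, but neither document gives a grade, a multiple of a limit or a size of change. What does exist is a reference range from every site: "all local laboratories will provide the required certificates and laboratory reference values".

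The investigator knows the arm. Protocol 3.2 explains: "Open design was chosen because of differences in the pharmaceutical forms". Protocol 4.4 and 6.11 place randomization before the laboratory results are available, so Day 1 labels can also be set with the arm known.

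**The concern.** A measured laboratory value does not depend on who reads it, which is useful in an open-label trial. A test on CS labels gives up that advantage: two identical sets of results can yield different counts if abnormal values are judged more readily significant under one drug than under the other. Objective out-of-range status is tabulated (Tables 9.19, 9.21, 9.23 and 9.25 show non-significant, significant and normal counts by arm) but not tested.

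The adverse event analysis is not an independent check. Protocol 6.12.11 says: "new or worsened clinically significant abnormalities shall be reported as adverse events in source documents and CRF". The same label therefore feeds the preferred-term permutation test in SAP 7.3.1 and the Fisher tests in Table 9.33.

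The second issue is direction. For a parameter that can be abnormal either way, one undirected row adds highs to lows. A drug effect in one direction is then compared against background from both.

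What is at stake is how the laboratory p-values in the safety section are read.

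**Working it through.** **1. Which laboratory shells carry a between-arm p-value**

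| SAP shells | Content | Between-arm p-value | Depends on CS label | Shows direction |
|---|---|---|---|---|
| 9.19, 9.21, 9.23, 9.25 | Non-significant / CS / normal counts | No | Partly | No |
| 9.20, 9.22, 9.24, 9.26 | CS counts only | Yes, per panel and visit | Entirely | No |
| 9.27 (9.28 to 9.30 marked as similar) | Values and change from baseline | No | No | Yes |

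The tested tables are the label-dependent, undirected ones. The label-free, signed tables have no test.

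**2. Arm size for the illustrations**

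The documents give no figure for the laboratory tests, so the planned arm size is used. Protocol 9.2 reproduces: (1.96 + 0.84)² × (0.70 × 0.30 + 0.70 × 0.30) / 0.20² = 7.84 × 0.42 / 0.04 = 82.3 per arm; 82.3 / 0.9 = 91.5, so 92 per arm and 184 in total. That figure is not in dispute.

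All rates and counts below are assumptions. Each test is a two-sided Fisher exact test on one parameter with 92 per arm. It stands in for the planned set-level permutation test and does not reproduce it.

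**3. Labelling**

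Let the true out-of-range rate a be the same in both arms, and let a fraction L of out-of-range patients be labelled CS. The CS probability is a × L; for a = 20% and L = 40% v 60% it is 8% v 12%. The chance that Fisher's test gives p ≤ 0.05, although the laboratory findings have the same distribution in both arms, is:

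| Out-of-range rate, both arms | L 50% v 50% | 40% v 60% | 30% v 70% | 20% v 80% |
|---|---|---|---|---|
| 10% | 1.9% | 4.3% | 13% | 33% |
| 20% | 2.7% | 9.6% | 35% | 73% |
| 30% | 3.1% | 16% | 56% | 92% |

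With few abnormal values, the counts can be distorted without the test reacting. If 10 patients per arm are out of range and 10% v 50% are labelled CS, the counts are 1 v 5, p = 0.21.

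**4. Direction**

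- Directional effect, highs only: 8 v 1, p = 0.035.
- The same with one low value added to each arm: 8 + 1 = 9 v 1 + 1 = 2, p = 0.058. This is dilution.
- Limiting case, equal and opposite: 8 high and 1 low v 1 high and 8 low gives 9 v 9, p = 1.00, although the highs alone are 8 v 1.

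Dilution applies to parameters that can be abnormal in both directions, such as white cells, neutrophils or platelets. It matters little for ALT, AST, urine nitrites or sediment counts, so this part is weaker for Tables 9.24 and 9.26. The labelling issue applies to all four tables.

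**The case against.** The strongest reply is that little hangs on these p-values. No safety hypothesis, alpha or stopping rule is tied to them. Protocol 9.8 plans descriptive laboratory tables with change from baseline. SAP 7.3.2 and Table 9.27 give signed, label-free summaries by arm, and SAP 7.3.7 adds listings, including one for patients with abnormal values. A shift in platelets would be visible there. Counting only clinically significant deviations is also a legitimate choice in acutely infected patients, many of whom may have trivial out-of-range values. All of this stands and limits the point to a minor one. It does not supply criteria for CS or a label-free comparison.

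Four stronger readings are tempting but not supported:

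- **That laboratory data are the only safety measure free of the assessor.** SAP 4.2 also lists spirometry and vital signs. FEV1 has a planned between-arm test (SAP 7.2.4.5), and vital signs are summarized as measured values.
- **That opposite effects will cancel.** Exact cancellation needs effects of equal size and opposite sign from the two drugs on the same parameter. Nothing in the documents suggests that.
- **That the Fisher p-values predict the planned result.** The planned test covers a whole panel, with 16 hematology entries listed. A Bonferroni correction of the 8 v 1 example gives 16 × 0.0345 = 0.55. The figures show mechanism only.
- **That the SAP orders highs and lows to be combined.** No sentence says so. Pooling is read from the undirected rule in 7.3.2 and from example shells, whose footnote lets the report's tables differ in form provided their meaning is kept.

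**Conclusion.** The point holds as a low-cost improvement. The only between-arm laboratory p-values depend on a label assigned without stated criteria by someone who knows the arm, and nothing in the plan keeps high and low apart. They can therefore mix labelling habits with laboratory findings and, for two-sided parameters, dilute a directional effect.

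The size cannot be fixed from the documents, which give neither abnormality rates nor labelling rates. Under the assumptions above, moderate differential labelling (40% v 60%) moves a single-parameter false rejection rate from about 2% to 3% up to about 4% to 16%. Larger differences do more, and sparse counts may show nothing. The documents do not show that differential labelling occurred; they show only that the test is open to it.

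The effect is confined to the reading of the laboratory p-values. The primary non-inferiority analysis does not use them.

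**What to change.** In SAP 7.3.2 and the laboratory shells:

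1. Classify each numeric result as Low, Normal or High against the local laboratory's reference range, and show the Day 1 to Day 8 shift by arm.
2. Add a between-arm permutation comparison per panel on these flags, with High and Low kept separate.
3. Use normal/abnormal for non-numeric urine items such as color and clarity, which do not fit a low/high scale.
4. Keep the CS comparison beside it, described as secondary and dependent on the investigator's label. Replacing it outright would be a debatable trade-off, because it carries the clinical judgement.
5. State that all laboratory p-values are descriptive.

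The cost is SAP wording, table shells and programming. Every laboratory already supplies its reference ranges, and no new data or visits are needed. The downside is that out-of-range values of no clinical importance enter the added comparison and there are more exploratory p-values. That is the reason for keeping the CS counts alongside and for item 5.

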**Table 9.22 Laboratory parameters. Biochemistry. CS deviations only. Safety population. N = xx**

Parameter	Day 1		Day 8\ET	
	Levopront®	Libexin®	Levopront®	Libexin®
Total protein				
CS deviation	xx (xx.x%)	xx (xx.x%)	xx (xx.x%)	xx (xx.x%)
Albumin				
CS deviation	xx (xx.x%)	xx (xx.x%)	xx (xx.x%)	xx (xx.x%)
...				
p-value		0.xxx		0.xxx

**Table 9.23 Laboratory parameters. Urinalysis. Deviation from normal values. Safety population. N = xx**

Parameter	Day 1		Day 8\ET	
	Levopront®	Libexin®	Levopront®	Libexin®
Color				
No data	xx (xx.x%)	xx (xx.x%)	xx (xx.x%)	xx (xx.x%)
CNS deviation	xx (xx.x%)	xx (xx.x%)	xx (xx.x%)	xx (xx.x%)
CS deviation	xx (xx.x%)	xx (xx.x%)	xx (xx.x%)	xx (xx.x%)
Normal	xx (xx.x%)	xx (xx.x%)	xx (xx.x%)	xx (xx.x%)
Clarity				
No data	xx (xx.x%)	xx (xx.x%)	xx (xx.x%)	xx (xx.x%)
CNS deviation	xx (xx.x%)	xx (xx.x%)	xx (xx.x%)	xx (xx.x%)
CS deviation	xx (xx.x%)	xx (xx.x%)	xx (xx.x%)	xx (xx.x%)
Normal	xx (xx.x%)	xx (xx.x%)	xx (xx.x%)	xx (xx.x%)
...				

**Parameters to be presented:** Color, Clarity, Specific gravity, pH, Protein, Glucose, Bilirubin, Urobilinogen, Ketone bodies, Nitrites, Hemoglobin.

**Table 9.24 Laboratory parameters. Urinalysis. CS deviations only. Safety population. N = xx**

Parameter	Day 1		Day 8\ET	
	Levopront®	Libexin®	Levopront®	Libexin®
Color				
CS deviation	xx (xx.x%)	xx (xx.x%)	xx (xx.x%)	xx (xx.x%)
Clarity				
CS deviation	xx (xx.x%)	xx (xx.x%)	xx (xx.x%)	xx (xx.x%)
...				
p-value		0.xxx		0.xxx

**Table 9.25 Laboratory parameters. Microscopic urine examination. Deviation from normal values. Safety population. N = xx**

Parameter	Day 1		Day 8/ET	
	Levopront®	Libexin®	Levopront®	Libexin®
Epithelium				
No data	xx (xx.x%)	xx (xx.x%)	xx (xx.x%)	xx (xx.x%)
CNS deviation	xx (xx.x%)	xx (xx.x%)	xx (xx.x%)	xx (xx.x%)
CS deviation	xx (xx.x%)	xx (xx.x%)	xx (xx.x%)	xx (xx.x%)
Normal	xx (xx.x%)	xx (xx.x%)	xx (xx.x%)	xx (xx.x%)
Erythrocytes				
No data	xx (xx.x%)	xx (xx.x%)	xx (xx.x%)	xx (xx.x%)
CNS deviation	xx (xx.x%)	xx (xx.x%)	xx (xx.x%)	xx (xx.x%)
CS deviation	xx (xx.x%)	xx (xx.x%)	xx (xx.x%)	xx (xx.x%)
Normal	xx (xx.x%)	xx (xx.x%)	xx (xx.x%)	xx (xx.x%)
...				

**Parameters to be presented:** Epithelium, Erythrocytes, Leukocytes, Casts, Bacteria, Salts.

**Table 9.26 Laboratory parameters. Microscopic urine examination. CS deviations only. Safety population. N = xx**

Parameter	Day 1		Day 8/ET	
	Levopront®	Libexin®	Levopront®	Libexin®
Epithelium				
CS deviation	xx (xx.x%)	xx (xx.x%)	xx (xx.x%)	xx (xx.x%)
Erythrocytes				
CS deviation	xx (xx.x%)	xx (xx.x%)	xx (xx.x%)	xx (xx.x%)
...				
p-value		0.xxx		0.xxx

**Table 9.27 Laboratory parameters. Hematology. Absolute values. Safety population. N = xx**

Parameter	Day 1 (baseline)		Day 8/ET or ED		Change at Day 8	
	Levopront®	Libexin®	Levopront®	Libexin®	Levopront®	Libexin®
Hemoglobin						
N	xx	xx	xx	xx	xx	xx
Mean (SD)	xx.x (xx.x)	xx.x (xx.x)	xx.x (xx.x)	xx.x (xx.x)	xx.x (xx.x)	xx.x (xx.x)
Median	xx.x	xx.x	xx.x	xx.x	xx.x	xx.x
Min – Max	xx.x – xx.x	xx.x – xx.x	xx.x – xx.x	xx.x – xx.x	xx.x – xx.x	xx.x – xx.x
Hematocrit						
N	xx	xx	xx	xx	xx	xx
Mean (SD)	xx.x (xx.x)	xx.x (xx.x)	xx.x (xx.x)	xx.x (xx.x)	xx.x (xx.x)	xx.x (xx.x)
Median	xx.x	xx.x	xx.x	xx.x	xx.x	xx.x
Min – Max	xx.x – xx.x	xx.x – xx.x	xx.x – xx.x	xx.x – xx.x	xx.x – xx.x	xx.x – xx.x
...						

**Parameters to be presented:** Hemoglobin, Hematocrit, RBC, WBC, Neutrophils (abs), Lymphocytes (abs), Monocytes (abs), Eosinophils (abs), Basophils (abs), Platelets, ESR, Neutrophils (%), Lymphocytes (%), Monocytes (%), Eosinophils (%), Basophils (%).

**Table 9.28 Laboratory parameters. Biochemistry. Absolute values. Safety population. N = xx**

Similar

**Parameters to be presented:** Total protein, Albumin, Total cholesterol, Total bilirubin, Conjugated bilirubin, ALT, AST, Serum creatinine, Glomerular filtration rate.

**Table 9.29 Laboratory parameters. Urinalysis. Absolute values. Safety population. N = xx**

Similar

**Parameters to be presented:** Color, Clarity, Specific gravity, pH, Protein, Glucose, Bilirubin, Urobilinogen, Ketone bodies, Nitrites, Hemoglobin.

**Table 9.30 Laboratory parameters. Microscopic urine examination.**  
**Absolute values. Safety population. N = xx**  
**Similar**

**Parameters to be presented:** Epithelium, Erythrocytes, Leukocytes, Casts, Bacteria, Salts.

**Table 9.31 Compliance. Safety population. N = XX**

	Levopront ® N = XX	Libexin ® N = XX
Compliance		
N	xx	xx
Mean (SD)	xx.x (xx.x)	xx.x (xx.x)
Median	xx.x	xx.x
Min – Max	xx.x – xx.x	xx.x – xx.x

**Table 9.32 Adverse Events (including SAE) started before the first dose of the study drug(s). Safety population. N = xx**

MEDDRA System Organ Class term MEDDRA Preferred term	Levopront ® (T) n (%)		Libexin ® (C) n (%)	
	x (%)	Y	x (%)	Y
SOC term	xx (xx.x)	xx	xx (xx.x)	xx
Preferred term 1	xx (xx.x)	xx	xx (xx.x)	xx
Preferred term 2	xx (xx.x)	xx	xx (xx.x)	xx
...				

X = Number of subjects having at least one AE from the group.  
 % = Percent of patients having at least one AE from the group  
 Y = Total number of events

**Table 9.33 Adverse events. Summary table. Safety population. N = XX**

Parameter	Levopront ® N = XX	Libexin ® N = XX	p-value Fisher test
Patients with AE/SAE	xx (xx.x%)	xx (xx.x%)	0.xxx
Patients with SAE	xx (xx.x%)	xx (xx.x%)	0.xxx
Patients with death outcome AE/SAE	xx (xx.x%)	xx (xx.x%)	0.xxx
Patients with mild and moderate AE/SAE	xx (xx.x%)	xx (xx.x%)	0.xxx
Patients with severe AE/SAE	xx (xx.x%)	xx (xx.x%)	0.xxx
Patients with related (possible probable or highly probable) AE/SAE	xx (xx.x%)	xx (xx.x%)	0.xxx
Patients with AE/SAE led to discontinuation	xx (xx.x%)	xx (xx.x%)	0.xxx

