6.12.4 Assessment of AE Severity

For each AE, the Investigator will assess the severity grade. For that purpose the following severity grading scale is used:

1. Mild	Grade 1 - does not interfere with patient's usual function (awareness of symptoms or signs, but easily tolerated [acceptable]).
2. Moderate	Grade 2 - interferes to some extent with patient's usual function (enough discomfort to interfere with usual activity [disturbing]).
3. Severe	Grade 3 - interferes significantly with patient's usual function (incapacity to work or to do usual activities [unacceptable])

For each episode, the highest severity grade attained should be reported.

It should be noted that severe AEs not always comply with criteria of seriousness, while SAE is not always severe. The urgency of reporting of SAE does not depend on the severity of the event.

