#### **4.2 SAFETY ENDPOINTS**

Rate of Adverse events (AE) and Serious Adverse Events (SAE) of the various severity according to subjective complaints, laboratory test results, physical examination, vital signs and spirometry.

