**Table 9.34 Adverse Events (including SAE). Safety population. N = xx**

MEDDRA System Organ Class term MEDDRA Preferred term	Levopront ® (T) n (%)		Libexin ® (C) n (%)	
	x (%)	Y	x (%)	Y
SOC term	xx (xx.x)	xx	xx (xx.x)	xx
Preferred term 1	xx (xx.x)	xx	xx (xx.x)	xx
Preferred term 2	xx (xx.x)	xx	xx (xx.x)	xx
...				

X = Number of subjects having at least one AE from the group.  
 % = Percent of patients having at least one AE from the group  
 Y = Total number of events

p-value = 0.xxx

Table 9.35 Adverse Events (including SAE) and severity.

Safety population. N = xx

MEDDRA System Organ Class term MEDDRA Preferred term	Severity	Levopront® (T)		Libexin® (C)	
		n (%) x (%)	Y	n (%) x (%)	Y
SOC term		xx (xx.x)	xx	xx (xx.x)	xx
Preferred term 1	Mild	xx (xx.x)	xx	xx (xx.x)	xx
Preferred term 2	Moderate	xx (xx.x)	xx	xx (xx.x)	xx
...					

X = Number of subjects having at least one AE from the group.

% = Percent of patients having at least one AE from the group

Y = Total number of events

Table 9.36 Adverse Events (including SAE) and relation to study drug(s).

Safety Set. N = xx

Similar

Table 9.37 Serious Adverse Events (only). Safety population. N = xx

MEDDRA System Organ Class term MEDDRA Preferred term	Levopront® (T)		Libexin® (C)	
	n (%) x (%)	Y	n (%) x (%)	Y
SOC term	xx (xx.x)	xx	xx (xx.x)	xx
Preferred term 1	xx (xx.x)	xx	xx (xx.x)	xx
Preferred term 2	xx (xx.x)	xx	xx (xx.x)	xx
...				

X = Number of subjects having at least one AE from the group.

% = Percent of patients having at least one AE from the group

Y = Total number of events

Table 9.38 Serious Adverse Events (only) and severity.

Safety population. N = xx

MEDDRA System Organ Class term MEDDRA Preferred term	Severity	Levopront® (T)		Libexin® (C)	
		n (%) x (%)	Y	n (%) x (%)	Y
SOC term		xx (xx.x)	xx	xx (xx.x)	xx
Preferred term 1	Mild	xx (xx.x)	xx	xx (xx.x)	xx
Preferred term 2	Moderate	xx (xx.x)	xx	xx (xx.x)	xx
...					

X = Number of subjects having at least one AE from the group.

% = Percent of patients having at least one AE from the group

Y = Total number of events

Table 9.39 Serious Adverse Events (only) and relation to study drug(s).

Safety Set. N = xx

Similar

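### The SAP's only overall severity comparison merges mild with moderate adverse events, so no summary or tested row shows the patient-level rate of moderate-or-worse events

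*SAP*

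**What the plan says.** SAP 4.2 defines the safety endpoint as "Rate of Adverse events (AE) and Serious Adverse Events (SAE) of the various severity", so severity belongs to the endpoint itself.

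Protocol 6.12.4 uses three grades. Mild means "awareness of symptoms or signs, but easily tolerated [acceptable". Moderate means "enough discomfort to interfere with usual activity [disturbing". Severe is the incapacitating grade above these.

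SAP Table 9.33 summarises patients in seven rows, each under a column headed "p-value Fisher test". Two of the rows concern severity: "Patients with mild and moderate AE/SAE" and "Patients with severe AE/SAE". There is no moderate row and no row for moderate or worse. Neither the table nor SAP 7.3.1 says how to place a patient who has events of more than one grade.

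Table 9.35, "Adverse Events (including SAE) and severity", and Table 9.38 (serious events only) show severity within system organ class and preferred term. Both give patients and events per arm, and their shells carry no p-value. SAP 7.3.1 also plans one permutation p-value for adverse events, based on preferred-term frequencies and not on grade.

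**The concern.** The merged row crosses the line the protocol draws between tolerable events and events that disturb daily activity. In a seven-day trial of a cough medicine it is plausible that nearly all events are mild or moderate, although the documents give no expected rates by grade. The merged row would then be close to the any-event row and the severe row close to zero. Table 9.33 would contain two severity rows and no usable comparison of severity.

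The missing counting rule adds an ambiguity. Protocol 6.12.4 records the highest grade per episode, while Protocol 6.12.3 treats a worsening of an ongoing event as a new event. A reaction that goes from mild to severe puts the patient in both severity rows if patients are counted on having at least one such event. At worst grade the patient is in the severe row only. Two programmers could produce different tables from the same data.

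**Working it through.** **Arm size.** Table 9.33 contains no figures, so the planned arm size is used. Inputs from Protocol 9.2: z = 1.96 and 0.84, 70% response in both arms, margin 20 points, early discontinuation up to 10%.

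- n per arm = (1.96 + 0.84)² × (0.7 × 0.3 + 0.7 × 0.3) / 0.20² = 7.84 × 0.42 / 0.04 = 82.32
- 82.32 / (1 − 0.10) = 91.5, rounded up to 92 per arm, 184 in total. The plan's figure is reproduced.

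**Illustration.** All event counts are assumed. Tests are two-sided Fisher exact tests with 92 per arm. Each arm has 12 patients with any event and none with a severe event. By worst grade, arm A has 11 mild and 1 moderate; arm B has 4 mild and 8 moderate.

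| Row | Arm A | Arm B | p |
|---|---|---|---|
| Any event (planned) | 12 | 12 | 1.00 |
| Mild and moderate (planned) | 11 + 1 = 12 | 4 + 8 = 12 | 1.00 |
| Severe (planned) | 0 | 0 | 1.00 |
| Moderate or severe (not planned) | 1 (1.1%) | 8 (8.7%) | 0.035 |

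For the last row, 9 of 184 patients have such an event. The chance that one given arm has 0 or 1 of the 9 is 0.00159 + 0.01568 = 0.01727, and doubling gives 0.0345.

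**Sensitivity to the assumed counts.**

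- 1 v 7 gives p = 0.064, and 2 v 8 gives p = 0.10.
- With 20 v 20 patients having any event and none severe, moderate 15 v 3 gives p = 0.005 and 11 v 3 gives p = 0.048. The merged row stays at 20 v 20, p = 1.00, in both cases.

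The p-value depends on the counts chosen. The cancellation in the merged row does not: whenever no patient has a severe event, that row equals the any-event row.

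**Can Table 9.35 supply the missing count?** Its patient numbers are given per preferred term. Suppose eight terms each show one patient with a moderate event. That fits eight patients with one event each, and equally four patients with two terms each. The number of patients with a moderate-or-worse event therefore cannot be obtained by adding rows.

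**The case against.** The strongest reply is that the severity information is not lost. Table 9.35 separates mild from moderate, its event counts can be added across terms, and SAP 7.3.7 plans listings of adverse events. Protocol 9.8 promises tabulation by term, relationship and severity, and Tables 9.35 and 9.38 deliver it. No passage requires a test of moderate events. Section 9 of the SAP contains example shells, and a footnote allows the final tables to differ provided their content is preserved.

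Most of this stands. A reader might infer that an excess of moderate events would be invisible in the whole report. The documents do not support that, because it could be seen term by term in Table 9.35. What is missing is the overall patient count and its comparison. The footnote permits adding them but commits nobody to do so.

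A reader might also infer that the merged row would make the more harmful arm look better. If 12 patients per arm have events and 4 v 0 have severe events only, the merged row reads 8 v 12 (p = 0.48). This needs patients whose events are all severe, or worst-grade counting, and Table 9.33 states no counting rule. The adjacent severe row would show 4 v 0 (p = 0.12), so the shift would be on the page even though it is not significant.

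Finally, the tests may have little to work on. Protocol 3.3.2 reports suspected adverse drug reactions in 2.1% of levodropropizine patients, and 0.021 × 92 is about 2 patients. Adverse events of any cause will be more frequent than that, but by how much is not stated. With very few events no layout gives an informative test, and seven unadjusted tests call for caution anyway. The descriptive count would still be worth having.

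**Conclusion.** The point holds as a gap in one safety summary. Table 9.33 is the only place where patients are counted and compared by severity across all terms, and it joins the two grades that the protocol distinguishes by effect on daily activity. If severe events are rare, its severity rows add almost nothing to the any-event row. A contrast such as 1 v 8 (p = 0.035) would then be reported in summary as 12 v 12 (p = 1.00). That size rests wholly on assumed counts and on two-sided tests at 92 per arm, and one patient fewer in the worse arm moves p to 0.064.

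The primary analysis, sample size and data collection are not affected. The change is worth making because severity is part of the stated safety endpoint and the cost is very small. Nothing here shows that Tables 9.35 or 9.38 are wrong.

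**What to change.** In SAP Table 9.33, replace the merged row by a row for patients with a moderate or severe event and keep the severe row, both with the planned Fisher test. Count each patient once, at the worst grade. Below these rows, show mild, moderate and severe by worst grade without tests. Add one sentence to SAP 7.3.1 stating the worst-grade rule for Table 9.33. Tables 9.35 and 9.38 can stay as they are.

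The cost is one table shell and one sentence, with no new data. The change should be made before database lock: the trial is open-label, and a severity cut-point added later would be post hoc.
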